Data Analytic Procedures: Since patients will be randomly assigned to the pregnenolone doses and placebo treatment groups, we do not expect the groups to be different on demographic, prior drug use history or other predictor variables. Nevertheless, prior to undertaking the specific analyses, we will compare the treatment groups on demographic variables, substance use characteristics and previous psychiatric history/predictor variables using t-tests/chi-square analyses as appropriate. If any group differences are found, the specific variable will be entered as a covariate in all of the specific analyses.

The laboratory study component proposes a 3 X 2 X 3 mixed-factorial design with Treatment (300mg Pregnenolone vs. 500mg Pregnenolone vs. Placebo) and Sex (AUD women vs. men) as the Between-Subjects factors and Imagery Condition (Stress, Drug Cues and Neutral cues) X Time Period 7 (Baseline, Image, Recovery 1, recovery 2, recovery3, Recovery 4 and Recovery 5) as the Within-Subjects factors. Order of imagery conditions will be randomly assigned and counterbalanced across subjects. As measurements for imagery condition and time period will be repeated within subjects, these are not independent, leading to correlations between measurements. Mixed linear models provide a way not only to model the mean differences between levels of factors, but also allows for modeling of the variancecovariance matrices (Laird and Ware 1982) (Littell, Milliken et al. 1996). This is particularly advantageous for designs such as the one proposed here which require repeated laboratory measurements within subjects. Furthermore, these models also have the capacity to handle missing data, without excluding subjects with missing data points (Cnaan et al., 1997; Littell et al., 1996).

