Thus, mixed linear models will be used to test the hypotheses for each of the specific aims. In each case, Subjects will be treated as a random effect and Sex, Imagery Condition and Timeperiod will be treated as fixed effects. PROC MIXED in the Statistical Analysis System (SAS, version 9.3) will be used to model the experimental effects. Each of the specific aims and hypotheses are listed below. For the treatment section of the study, Cox Proportional Hazards models will be used to ascertain differences in time to relapse between AUD individuals treated with pregnenolone compared with those treated with placebo. We anticipate that pregnenolone-treated individuals will demonstrate a survival function reflecting an increase in number of days to relapse compared to the placebo group.

Specific Aim #1: *To evaluate the safety/tolerability of 300mg and 500 mg/day of PREG vs PLA in AUD individuals. Hypothesis 1: PREG 300 and 500 mg/day will be found to be safe, well-tolerated and with fewer side effects/adverse events as compared to the PLA group. Statistics to test hypothesis 1 will compare safety and adverse events data using percentages of various side effects and number and type of AE's for the three treatment groups by each week in treatment using PROC MIXED procedures in SAS, but also frequencies of overall AEs compared across the 8-week period.*

Specific Aim #2a: To evaluate PREG dose (PLA, 300 and 500 mg/day) effects on ALLO and on provoked cue- and stress induced craving, HPA responses, anxiety/mood and cognitive flexibility in AUD patients.

Hypothesis 2a: Compared to PLA, PREG will dose dependently increase ALLO levels and also decrease stress and cue-induced alcohol craving, anxiety, normalize HPA axis basal and response levels of Cortisol, ACTH and adrenal sensitivity (Cortisol/ACTH ratio) and improve Stroop cognitive flexibility.

Specific Aim #2b: To assess whether PREG-stimulated ALLO levels mediate its effects on provoked craving, anxiety, mood, HPA axis response and cognitive flexibility in the laboratory component. Hypothesis 2b: Compared to PLA, higher ALLO levels in the PREG dose groups will mediate greater reductions in alcohol craving, anxiety, mood, cognitive flexibility and normalizing of HPA axis measures specified in Hypothesis 2a.

Specific Aim #3a: To determine the efficacy of 8-week PREG doses versus PLA treatment on primary alcohol use outcomes, and secondary outcomes including alcohol craving, anxiety and mood.

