Hypothesis 3a: AUD patients on PREG doses versus those on PLA will dose dependently show (a) Primary: higher alcohol abstinence days, lower mean heavy drinking days and lower amounts of alcohol used in the 8-week treatment period, and (b) secondary: lower alcohol craving, anxiety and negative mood symptoms.

Specific Aim #3b: To assess whether PREG-stimulated ALLO levels mediate its effects on primary alcohol use outcomes and on secondary clinical outcomes during the 8-week treatment phase. Hypothesis 3b: Compared to PLA, higher ALLO levels in the PREG dose groups will dose dependently mediate primary and secondary alcohol use outcomes predicted in the above Hypothesis 3a with the PREG 500mg group showing better primary and secondary outcomes than the PREG 300mg group who will be better than outcomes in the PLA group.

Exploratory Aim: To explore whether pre-treatment patient characteristics (gender, family history of alcoholism (FH), trauma history and co-morbid drug use) influence PREGpotentiated ALLO levels and primary and secondary alcohol use outcomes.

Exploratory analyses using mixed effects models and MRMs will be conducted to assess if pretreatment characteristics and laboratory responses (average or AUC) are predictive of primary alcohol use outcomes.

SECTION VI: RESEARCH INVOLVING DRUGS, BIOLOGICS, RADIOTRACERS, PLACEBOS AND DEVICES

If this section (or one of its parts, A or B) is not applicable, state N/A and delete the rest of the section.

A. DRUGS, BIOLOGICS and RADIOTRACERS

1. Identification of Drug, Biologic or Radiotracer: What is (are) the **name(s)** of the drug(s) biologic(s) or radiotracer(s) being used? Identify whether FDA approval has been granted and for what indication(s).

Pregnenolone is a naturally occurring steroid, which is available as a dietary supplement in health stores. **Under the Dietary Supplement Health and Education Act of 1994 (DSHEA), a dietary supplement is not considered a drug if the intended use is only to affect any function of the body.** In this pilot study, we are looking at pregnenolone's effect on function in the body and we will be collecting preliminary alcohol and drug use outcome data.

All protocols which utilize a drug, biologic or radiotracer **not** approved by, but regulated by, the FDA, or a radiotracer regulated by the RDRC, must provide the following information:

- a. What is the Investigational New Drug (IND) **number** assigned by the FDA?
- b. Who holds the IND?

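### Treatment-phase drinking (Hypothesis 3a) has several unreconciled analysis methods; as worded, neither the mixed model nor the Cox model yields a per-dose effect, and the primary outcome lists disagree

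*Combined protocol and SAP*

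**What the plan says.** All references are to the combined protocol and SAP.

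- **Section V.12, opening paragraph.** Comparison of the medication groups on primary outcomes will be mostly descriptive. Alcohol use measures in the treatment phase will be assessed with non-parametric tests. The findings are to supply effect sizes for a later, larger trial.
- **Section V.12, Data Analytic Procedures, mixed models.** "mixed linear models will be used to test the hypotheses for each of the specific aims". The sentence that follows applies to every case: subjects are random, and "Sex, Imagery Condition and Timeperiod will be treated as fixed effects".
- **Same heading, Cox model.** For the treatment section, "Cox Proportional Hazards models will be used to ascertain differences in time to relapse". The contrast is worded with two groups only: "between AUD individuals treated with pregnenolone compared with those treated with placebo".
- **Same heading, laboratory design.** "The laboratory study component proposes a 3 X 2 X 3 mixed-factorial design with Treatment (300mg Pregnenolone vs. 500mg Pregnenolone vs. Placebo"; the other between-subjects factor is Sex. The time periods are baseline, image and five recovery points.
- **Hypothesis 1.** Adverse events are compared "for the three treatment groups by each week in treatment using PROC MIXED procedures in SAS".
- **Hypothesis 3a.** The primary outcomes are "higher alcohol abstinence days, lower mean heavy drinking days and lower amounts of alcohol used in the 8-week treatment period", with a dose-dependent effect expected; craving, anxiety and negative mood are secondary. Hypothesis 3b spells out the ordering: "PREG 500mg group showing better primary and secondary outcomes than the PREG 300mg group who will be better than outcomes in the PLA group".
- **Section V.3, Individual Counseling.** Alcohol use, mood, stress and craving are all primary, measured by MetricWire and urines.
- **Section V.12, outcome lists.** Alcohol use (weekly urine screens and the Substance Use Calendar), SAFTEE events and adherence are primary. Craving and the perceived stress scale are secondary.
- **Section V.7, inclusion criterion ii.** Evidence of recent alcohol use is required. No abstinence period is stated.

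**The concern.** Aim 3a is the efficacy aim, and its three drinking measures need one stated route from data to estimate. The plan offers several, with no order among them, and each model-based route has a gap when followed as written. The mixed model has no treatment term for the 8-week phase. The Cox model addresses an event that appears in no outcome list, and its contrast does not distinguish the doses.

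Two things are at stake. First, the next trial would need an effect size for each dose, and neither model as worded gives one for the Hypothesis 3a measures. Second, with several methods, differing primary lists and two sources for the alcohol measure, the choice of which result counts as the efficacy finding is left open until the data are seen.

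**Working it through.** The plan gives no alpha, power, event rate or effect size for this analysis, so there is no stated figure to reproduce. The check is a comparison of the text, followed by two illustrations on assumed inputs.

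**1. Mixed model.** The fixed-effects sentence covers all aims and lists three factors.

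| Factor | Laboratory sessions | 8-week drinking |
|---|---|---|
| Sex | yes | yes |
| Imagery Condition | yes | does not exist; the sessions are in week 2 only |
| Time period | defined (baseline to Recovery 5) | not defined |
| Treatment | missing here, but supplied by the laboratory design sentence | missing, and supplied nowhere |

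Hypothesis 1 shows the kind of sentence required (three groups, by week). Hypothesis 3a has none.

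**2. Cox contrast.** The hypotheses order three groups and the Cox sentence names two. To see what a two-group contrast can show, assume three equal arms, exponential times to relapse, censoring at day 56 and a placebo hazard h of 0.01, 0.02 or 0.05 per day. Let S0, S300 and S500 be the survival functions, A = S300 + S500, e0 = h·S0 and e1 = h·(HR300·S300 + HR500·S500). The large-sample pooled hazard ratio θ solves

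∫ from 0 to 56 of { e1 − (e0 + e1)·θA/(θA + S0) } dt = 0.

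| True HR, 300 mg / 500 mg | θ at h = 0.01 | 0.02 | 0.05 |
|---|---|---|---|
| 0.70 / 0.70 (equal) | 0.700 | 0.700 | 0.700 |
| 0.85 / 0.56 (ordered) | 0.700 | 0.695 | 0.687 |
| 1.00 / 0.45 (300 mg inert) | 0.706 | 0.690 | 0.663 |
| 0.45 / 1.00 (reversed) | 0.706 | 0.690 | 0.663 |

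The last two rows are identical by symmetry. At h = 0.02 with 300 mg inert, relapse by day 56 is 1 − exp(−0.02 × 56) = 67.4% on placebo and on 300 mg, and 1 − exp(−0.02 × 0.45 × 56) = 39.6% on 500 mg. The pooled 0.69 shows none of that.

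**3. Undefined relapse.** Participants need not be abstinent at entry, so relapse might mean a first drink, a first heavy day or a return after a period of abstinence. Treat it as a first event with daily probability p. The share of 56-day events that fall in week 1 is [1 − (1−p)^7] / [1 − (1−p)^56].

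- p = 0.02: 0.132 / 0.677 = 19%.
- p = 0.50: 0.992 / 1.000 = 99%.

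If p varies between people as a beta distribution with mean p and a + b = 1, 2 or 4, each probability becomes 1 − B(a, b+n)/B(a, b), with n = 7 or 56. The share is then 42% to 58% at p = 0.02 and 86% to 94% at p = 0.50. Whether the Cox result mostly describes week 1 or the whole 8 weeks depends on a definition that the plan does not give.

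**4. Outcome lists.**

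| | Section V.3 | Section V.12 lists | Specific Aim 3a / Hypothesis 3a |
|---|---|---|---|
| Craving | primary | secondary | secondary |
| Mood | primary | not in either list as such | secondary |
| Stress | primary (MetricWire) | secondary (perceived stress scale) | not listed |
| Source of alcohol measure | MetricWire, urines | urines, Substance Use Calendar | not stated |

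The conflict on craving and mood is firm. On stress it is weaker, because the instruments differ.

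**The case against.** **The Treatment omission looks like a slip.** The fixed-effects list follows directly from the laboratory design, which has three-level Treatment, and the opening of Section V.12 says the mixed models assess treatment group differences. This largely stands for the laboratory aims. It does not repair Aim 3a, for which no sentence supplies Treatment or a week factor.

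**The doses are not expressly pooled.** This is correct. A two-group contrast is the natural reading, but a dose-coded Cox model is not excluded. The supportable statement is that the wording does not separate the doses.

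**The plan still yields arm-level drinking results.** This also stands. A reader might infer that the trial has no analysis of treatment effects on drinking. The documents do not support that: the descriptive comparisons and non-parametric tests cover alcohol use and could compare the arms, though only crudely and without stated contrasts.

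**It is a pilot.** Sections V.11 and V.12 describe a pilot efficacy study and preliminary data. That lowers the stakes but does not reconcile the methods, because the same section states hypotheses to be tested and promises effect sizes for the next trial.

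**The illustrations prove little.** The first is true almost by construction, and the second rests on invented probabilities. They show what the wording leaves undetermined. They do not measure error in this trial.

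**Conclusion.** The point holds and should be fixed. Four methods reach treatment-phase drinking with no precedence. The mixed model as written has no treatment term for Aim 3a. The Cox contrast as worded cannot address the hypothesised dose ordering and uses an undefined event. The primary status of craving and mood, and the source of the alcohol measure, conflict between sections.

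The harm is limited to how Aim 3a can be interpreted and to per-dose effect sizes for the later trial. A reader might go further and conclude that a confirmatory efficacy claim is invalid. The plan makes no such claim, so that does not follow.

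The textual findings need no assumption beyond reading the Cox sentence as a two-group contrast. The pooled hazard ratios (0.66 to 0.71 across four different dose patterns) and the week-1 shares (19% to 99%) rest wholly on assumed hazards and daily probabilities.

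**What to change.** 1. **Model (Section V.12, Data Analytic Procedures).** Add Treatment (placebo, 300 mg, 500 mg) to the fixed effects and limit Imagery Condition to the laboratory aims. Give Hypothesis 3a its own sentence: for each drinking measure, a repeated-measures model suited to bounded or skewed counts, with Treatment, Week, Treatment-by-Week and Sex. Adjust for the matching measure from the 90-day pre-treatment calendar, and name the distribution and link in advance. Report each dose versus placebo averaged over weeks 1–8 (3 measures × 2 doses = 6 estimates). Add a 500-versus-300 contrast, or a linear dose trend, for the ordering (3 more), since dose-versus-placebo contrasts alone do not test it. Give all as estimates with confidence intervals. State that this governs for alcohol use and that the non-parametric tests there become a sensitivity analysis. The non-parametric tests for side effects, CIWA and perceived stress are unaffected.
2. **Outcomes (Section V.3, and item 1 of the Section V.12 primary list).** Align both with Hypothesis 3a: the three drinking measures from the Substance Use Calendar are the primary efficacy outcomes; urine and MetricWire drinking data are supportive; mood, stress and craving are secondary. The safety and adherence primaries stay.
3. **Cox.** Separate the dose arms, define the relapse event, time origin and censoring rule, and label the analysis exploratory; or drop it.

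The cost is wording and slightly more analysis work. The daily drinking data are already planned. The survival analysis loses its main role.

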We have developed and validated a laboratory-based imagery induction method that reliably increases alcohol craving after imagery of stressful and drug cue events in individuals with alcohol use disorder (Sinha et al., 1999; 2000). However, whether a neuroactive steroid suppresses stress and alcohol-induced craving in individuals with alcohol use disorder has not been directly tested. In a sample of 90 treatment seeking men and women with alcohol use disorder, we will examine the effects of PREG on alcohol craving, alcohol motivation and intake, subjective mood states, and neurobiological responses in personalized stressful imagery and drug cues imagery. All subjects will be exposed to three imagery sessions (neutral, stressful and drug cues) and the order of imagery conditions will be counterbalanced across subjects.

We've selected PREG, because it is the precursor to potent neuroactive steroids, such as ALLO, and because it is easily available as a dietary supplement. We selected 300mg/day and 500 mg/day dosing based on prior clinical trials of PREG in psychiatric patients. In an 8-week clinical trial in schizophrenia patients, fixed escalating dosing from 100mg to 500mg of PREG (Marx et al., 2009) was well tolerated. The only side effects present in the PREG group to a greater degree than the PLA group were two reports of mild restlessness, one report of mild muscle pain/stiffness, and one report of mild cold extremities. A follow-up randomized clinical trial in men and women with schizophrenia used escalating doses of PREG, 100mg for 2 weeks, 300mg for 2 weeks, 500mg for 4 weeks, and found PREG to be safe and well tolerated (Marx et al., 2014). A 12-week randomized placebo-controlled trial of escalating doses of PREG to 400mg daily for 4 weeks in men and women with bipolar depression improved depressive symptoms and showed PREG to be safe and well tolerated in all patients (Brown et al., 2014). A recent study using an acute dose of PREG of 400mg to examine its effects on emotion regulation neurocircuitry (Sripada et al., 2013), also didn't find any side effects.

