3. **Research Plan:** Summarize the study design and research procedures using non-technical language that can be readily understood by someone outside the discipline. **Be sure to distinguish between standard of care vs. research procedures when applicable, and include any flowcharts of visits specifying their individual times and lengths.** Describe the setting in which the research will take place.

1. Study Design and Overview

Ninety treatment seeking men and women with AUD will be recruited to participate in and complete this preliminary study. Participants will be recruited through flyers and advertisements in local newspapers and from community substance abuse treatment facilities. Subjects will participate in an initial screening and intake session to obtain informed consent, followed by physical examination and blood work to determine eligibility. Eligible

participants will be randomly assigned to 2 doses of PREG (300/500 mg/day) vs placebo (PLA) treatment (N=30/group) over 8 weeks. In week 2, AUD patients will participate in a 3day human laboratory study where they will be exposed to three experimental sessions of stress, alcohol cue and neutral-relaxing imagery on separate days (Fox et al.,2007; 2009; Sinha et al., 2008; 2009; 2011). Throughout the study, participants will come twice-weekly to the Yale Stress Center to receive medication, counseling and provide urine samples for UTOX. Women will be enrolled during the mid-luteal phase of the menstrual cycle so that laboratory sessions will be scheduled during the early to mid-follicular phase of the cycle when endogenous sex hormone levels are low prior to ovulation. PREG doses and matching placebo will be obtained by Yale IDS for compounding and dosing to 300mg and 500mg of PREG or PLA. Participants will self-administer study medication on a twice-daily dosing schedule throughout entire study.

Subjects will begin with full respective dose of medication immediately without a titration period, as previous studies with similar doses of pregnenolone up to 500 mg/day at b.i.d. dosing to be well tolerated and with no side effects (Marx et. al., 2009; Marx et al., 2014; Brown et al., 2014; Sripada et al., 2013).

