Reporting of Other Study-Safety Events: The project PI will inform the Data Safety Monitor, the Yale HIC, NIDA project officer and the sponsor promptly of any change in recruitment or other changes in this project that are relevant to safety, as well as any action taken by the Yale HIC as a result of continuing review of this project.

12. Statistical Considerations: Describe the statistical analyses that support the study design. For this preliminary study data we will mostly use descriptive statistics for comparing the medication groups on primary outcome measures and safety measures. Repeated measures ANOVA and mixed model procedures to assess treatment group differences in alcohol craving and stress related arousal (heart rate, blood pressure, HPA and catecholamine responses) during laboratory exposure to stress and drug cues as compared to neutral imagery conditions. Non-parametric tests will be used to assess occurrence of side effects, alcohol use measures, CIWA scores and perceived stress scores during the treatment study phase. The number and type of AE's for the two medication groups will be conducted using t-tests, chisquare tests and ANOVAs as appropriate. Findings will be used to estimate effect sizes for the medication and guide the larger randomized clinical trial in the future.

Primary Outcome Measures during 8 week treatment: The primary outcome measures will be:(1) alcohol use as measured by weekly urine drug screens and self-report of drug use on the Substance Use Calendar, (2) side effects and adverse events as measured by the SAFTEE, and (3) treatment adherence as measured by frequency of attendance for medication selfadministration and attendance for counseling appointments, including missed sessions.

Secondary Outcome Measures: Secondary outcome measures will include alcohol craving scales, alcohol withdrawal assessment using the CIWA, perceived stress scale, the recent stressful life events scale (LES), and the COPE Questionnaire. In addition, other assessments will be used to ensure that medications groups are not different in various measures at baseline and also to assess their role in predicting treatment response. Examples of such

assessments would be demographic measures, depressive and anxiety symptoms, motivation to change and thoughts about abstinence, which are measures that have been found to predict substance abuse treatment outcomes (Hall et al., 1990; 1991; McMahon et al., 1986).

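### Hypothesis 1 predicts that pregnenolone is safe with fewer adverse events than placebo, but cites no rate behind 'fewer', sets no criterion for 'safe', and compares arms of 30 that can settle neither

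*Combined protocol and SAP*

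**What the plan says.** Specific Aim 1 is to evaluate safety and tolerability of the two doses. In Section V.12 (Statistical Considerations), Hypothesis 1 makes this a directional prediction: "PREG 300 and 500 mg/day will be found to be safe, well-tolerated" and "with fewer side effects/adverse events as compared to the PLA group". The test follows directly: "Statistics to test hypothesis 1 will compare safety and adverse events data using percentages of various side effects and number and type of AE's", by week with PROC MIXED for three treatment groups, plus overall frequencies across the 8 weeks.

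The opening paragraph of Section V.12 adds significance tests: "The number and type of AE's for the two medication groups will be conducted using t-tests, chisquare tests and ANOVAs as appropriate". It counts two medication groups where Hypothesis 1 counts three. The list of primary outcomes in the same section includes "side effects and adverse events as measured by the SAFTEE".

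On size, Section V.3 (Study Design and Overview) says that participants will be "randomly assigned to 2 doses of PREG (300/500 mg/day) vs placebo (PLA) treatment (N=30/group) over 8 weeks". No power or precision calculation accompanies this figure.

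The same opening paragraph of Section V.12 also calls the study preliminary, says that primary and safety measures will be compared mostly by descriptive statistics, and says that the findings are meant to give effect sizes for a larger trial.

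**The concern.** There are three gaps between the aim and its hypothesis.

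- **Direction.** Evaluating safety does not require showing fewer events than placebo. The documents cite no AE rate, in this population or another, that would lead one to expect fewer.
- **Criterion.** 'Safe' and 'well tolerated' have no definition, acceptable rate or margin, and no confidence interval is planned. The between-arm comparison is the only test attached to either word.
- **Information.** With 30 per arm, that comparison is weak in both directions. It would seldom confirm a real reduction and seldom flag a real excess, and a numerically lower count on drug is common by chance.

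AEs are a named primary outcome, and the results are meant to guide a larger trial. A safety statement that goes further than 30 per arm can support would carry over into that trial's planning.

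**Working it through.** **Inputs from the documents.** 30 per arm and 3 × 30 = 90 in total (Section V.3; Section VII.1). The arithmetic agrees, but the sample size cannot be derived: the documents give no AE rate, significance level, power, effect size or margin.

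**Assumptions.** Two-sided 5% level, one dose against placebo, and the proportion of patients with at least one event of a given kind. AE risks of 10% to 70% are assumed, to show a range.

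**Step 1. Power, 30 against 30.** For each pair of true risks, sum the binomial probabilities of all outcomes (i of 30, j of 30) that reach p ≤ 0.05. The plan names chi-square tests without saying whether they are corrected. Uncorrected chi-square is the favourable end and Fisher's exact test the conservative end.

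| Question | True risks | Fisher | Chi-square |
|---|---|---|---|
| Excess on drug | 10% placebo, 20% drug | 9.6% | 19% |
| Excess on drug | 10% placebo, 30% drug | 37% | 50% |
| Halving on drug | 20% placebo, 10% drug | 9.6% | 19% |
| Halving on drug | 50% placebo, 25% drug | 41% | 52% |
| Halving on drug | 70% placebo, 35% drug | 71% | 80% |

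A doubling from 10% to 20% is therefore missed at least four times in five under either test.

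**Step 2. Numerically fewer by chance.** With equal true risks (10% to 70%), the probability that a given dose arm has fewer affected patients than placebo is the sum over i < j of P(X = i)·P(Y = j), with both counts binomial(30, p). It is 41% to 45%. Both dose arms come out lower 26% to 28% of the time.

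**Step 3. Precision of a risk difference.** With equal risk p in the two arms, the 95% half-width is 1.96 × √(2p(1−p)/30).

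- p = 10%: 1.96 × √(2 × 0.1 × 0.9/30) = 0.152, about 15 points
- p = 20%: 0.202, about 20 points
- p = 30%: 0.232, about 23 points
- p = 50%: 0.253, about 25 points

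For example, 3 of 30 in each arm gives an observed difference of zero but an interval of about −15 to +15 points.

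**Step 4. Zero events in one arm.** The exact upper limit for the true rate solves (1−p)^30 = α.

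- One-sided 95%: 1 − 0.05^(1/30) = 0.095, or 9.5%
- Two-sided 95%: 1 − 0.025^(1/30) = 0.116, or 11.6%

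The absence of a serious event in a dose arm would still be compatible with a true rate near one in ten.

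**The case against.** **The study is a pilot and says so.** Section V.12 promises mostly descriptive statistics and effect-size estimates, Aim 1 is worded as an evaluation, and per-arm percentages are already planned. This stands, and it lowers the weight of the point. It does not remove it: the same section still sets a safe-and-fewer hypothesis, names tests for it, and plans neither intervals nor a bounded conclusion.

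**No rule equates non-significance with safety.** A reader might infer that a null AE comparison would be reported as proof of safety. The documents do not say this. Hypothesis 1 predicts fewer events, so a null result would strictly fail to support that part of it. The objection stands. The defect is an undefined 'safe' tied to an uninformative comparison, not a stated misuse of a p-value.

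**Other safety data exist.** Vital signs, laboratory chemistry, severity and attribution grading and quarterly review by the monitoring board are all described. They protect participants, but none has a criterion for Hypothesis 1.

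**The background does not contradict 'fewer'.** Section V.2 introduces its list with "The only side effects present in the PREG group to a greater degree than the PLA group" and names four mild complaints from one earlier trial. It is tempting to call this a conflict, but particular complaints can be commoner on drug while total events are fewer, and no overall rates are given. The supportable statement is that 'fewer' has no cited support.

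**Some scenarios are adequately powered.** A halving from 70% reaches up to 80% power pairwise, and about 90% with the doses pooled (30 against 60). This stands for very common events and a very large effect. Pooling does not rescue moderate rates (66% for a halving from 50%), is not planned, and leaves the 'safe' part untouched.

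**Conclusion.** The point holds as a mismatch between hypothesis and design. The prediction of fewer events has no cited rate behind it, 'safe' has no criterion, and 30 against 30 can neither establish safety nor reliably detect an excess. Power for a doubling from 10% is 10% to 19%. An observed difference of zero leaves an excess of about 15 to 25 points open, depending on the event rate. Zero events leaves a true rate of up to 9.5% (one-sided 95%) or 11.6% (two-sided 95%).

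The power figures and half-widths rest on assumed AE risks and a two-sided 5% level, because the documents give neither. The zero-event limits depend only on the 30 per arm and the chosen confidence level.

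The change should be made, but the point does not invalidate the trial. The stated preliminary, descriptive purpose is sound, and Hypothesis 1 is the part out of line with it.

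**What to change.** In Section V.12, delete the prediction of fewer events than placebo and restate Hypothesis 1 as estimation:

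- incidence of AEs in each of the three arms, overall and by type;
- risk difference of each dose against placebo, with a 95% interval;
- exact upper confidence limits for severe and for serious events in each arm;
- a sentence limiting any safety conclusion to the excess that the interval excludes.

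Use the same number of groups in the opening paragraph and under Hypothesis 1.

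The cost is wording. No extra patients, visits or data are needed. The stated safety conclusion becomes less favourable, because it will have to show how large an excess remains possible.
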